## **2. Study Contact Personnel**

### 3. Study Synopsis

Prospective Multi-Center Single-Arm Study of the Reverse Medical Barrel® VRD for Adjunctive Treatment to Embolic Coils for Wide-neck, Intracranial, Bifurcating/Branching Aneurysms of Middle Cerebral and Basilar Arteries: “The BARREL Study”

Title:	The BARREL Study
Study Device:	Reverse Medical Barrel ® Vascular Reconstruction Device (“Barrel VRD”)
Purpose:	To evaluate the safety and effectiveness of the Reverse Medical Barrel ® VRD for Adjunctive Treatment to Embolic Coils for Wide-neck, Intracranial, Bifurcating/Branching Aneurysms of Middle Cerebral and Basilar Arteries.
Intended Use:	For use with embolic coils for the treatment of wide-neck bifurcating or branching intracranial MCA and basilar aneurysms arising from a parent vessel with a diameter of $\geq 2\text{mm}$ and $\leq 4\text{mm}$ . “Wide-neck” is defined as having a neck width $\geq 4\text{mm}$ or a dome-to-neck ratio $< 2$ .
Study Design:	The BARREL Study is a prospective multi-center, single-arm study of the Barrel ® VRD. A maximum of 159 patients will be enrolled (consented) at up to 28 centers to ensure 119 treated patients. After obtaining informed consent, screening and baseline assessments, and eligibility confirmation, qualifying patients will receive the study treatment.
Inclusion Criteria:	
 
• Male or female between 18 and 85 years old.
 
• A wide-neck aneurysm with a neck <math>\geq 4\text{mm}</math> or a dome-to-neck ratio <math>< 2</math>, that is also a bifurcating or branch MCA or basilar aneurysm and de novo or non-de novo MCA or basilar aneurysm where no stent was utilized.
 
• Subject's aneurysm arises from a parent vessel with a diameter <math>\geq 2\text{mm}</math> and <math>\leq 4\text{mm}</math>.
 
• Appropriate informed consent obtainable as determined by local IRB.
 
• Life expectancy <math>> 24</math> months.
 

Exclusion Criteria:	
 
• Aneurysm rupture within 30 days of enrollment.
 
• MCA or basilar bifurcating aneurysms not treatable with coiling.
 
• Subject with anatomy not accessible for Barrel VRD treatment.
 
• Aneurysm neck <math>> 8\text{mm}</math>.
 
• Subject presents with an intracranial mass or is currently undergoing radiation therapy for carcinoma of the head or neck region.
 
• Subject has additional aneurysms for which treatment is planned within 18 months.
 
• Subject has platelet count of <math>< 70,000</math>.
 
• Subject has had a previous intracranial stenting procedure associated with the target aneurysm.
 
• Subject has an International Normalized Ratio (INR) <math>\geq 1.7</math> or is on one of the following anti-coagulant/anti-platelet medications : Aggrenox, Cilostazol, Apixaban, Dabigatran, Fondaparinux, Lepirudin, Pradaxa, Rivaroxaban, Argatroban, Arixtra
 
• Subject has serum creatinine level <math>> 2\text{mg/dl}</math> at baseline screening.
 
• Subject has known allergies to nickel-titanium metal.
 
• Subject has known allergies to aspirin or heparin.
 
• Subject has a life-threatening allergy to contrast (unless treatment for allergy can be tolerated).
 
• Subject has a known cardiac disorder, likely to be associated with cardioembolic symptoms such as atrial fibrillation (AFIB).
 

	
 
• Subject has any condition, which in the opinion of the treating physician, would place the subject at a high risk of embolic stroke.
 
• Subject is currently participating in another clinical research study.
 
• Subject is pregnant or breastfeeding.
 
• Subject has participated in a drug study within the last 30 days.
 
• Subject cannot or is unwilling to take ASA and a P2Y12 Platelet Inhibitor as required by the protocol following the procedure.
 
• Subject is unable or unwilling to comply with protocol requirements and obtain required clinical evaluations and follow-up.
 

Evaluation Criteria:	
Primary Endpoints
 
 
• Primary Efficacy Endpoint: The number of Barrel® VRD treated aneurysms achieving Raymond Grade I (100% occlusion) at 12 months ± 8 weeks in the absence of retreatment, parent artery stenosis (> 50%), or target aneurysm rupture.
 
• Primary Safety Endpoint: Incidence of neurological death or major ipsilateral stroke (National Institutes of Health Stroke Scale [NIHSS] increase of ≥ 4 for >24 hours) at any time during the follow-up period (12 months ± 8 weeks).
 

	
Secondary Endpoints
 
 
• Any cause death within 30 days or neurological death within 12 months ± 8 weeks.
 
• Number of Barrel® VRD treated aneurysms achieving Raymond Grade I or II at 12 months ± 8 weeks in the absence of retreatment, parent artery stenosis (> 50%), or target aneurysm rupture.
 
• Number and percentage of successful device implants.
 
• Angiographic evidence of in-stent stenosis at 12 months ± 8 weeks reported according to the following ordinal groups: <25%, 25-50%, 51-75%, >75%.
 
• Device-related Serious Adverse Events (SAEs).
 
• The composite percentage of patients with modified Rankin Score of 0-2 or no change from baseline at 12 months ± 8 weeks.
 

Schedule of Tests:	The tests and evaluations to be conducted at baseline, procedurally, and during follow-up are summarized in Table 3-1.
Statistical Considerations:	The rate of the primary efficacy endpoint will be formally compared against a historical control. The study will be conducted at up to 28 centers, and it will enroll up to 159 subjects to ensure 119 subjects are treated/undergo attempted treatment. The statistical analysis plan is detailed in Section 6.

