**Table 3-1 Schedule of Tests**

Tests and Evaluations	Screening/ Baseline	Procedural (Day 0)	30 days ±14 days	180 days ±30 days	12 months ±8 weeks	Unscheduled Visit
Inclusion/Exclusion	X					
Demographics	X					
Medical history	X					
Medications	X	X	X	X	X	X
Blood Labs	X					
Modified Rankin Score	X		X	X	X	
NIHSS Score	X			X	X	X 
Adverse Events		X	X	X	X	X
Angiography 	X 	X		X 	X	
Raymond Grade Scale	X 	X		X	X	

MRA is acceptable if performed according to the standard of practice at the participating institution.

The baseline angiogram must be taken no more than 180 calendar days prior to the procedure.

For previously coiled aneurysms

If an angiogram is performed as standard patient care it should be sent to the core laboratory for analysis.

If visit is related to target aneurysm or potentially associated adverse event

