### 4.1 Summary of Changes

Revision A to Revision B		
Section	Change	Rationale
Sponsor	Sponsor name and study contacts changed from Reverse Medical to Covidien Neurovascular	Covidien acquired Reverse Medical and is executing the study
Study Design	Increased the number of participating centers from 20 to 28	Updated to facilitate enrollment
Exclusion criteria	Added exclusion criteria for subject with anatomy not appropriate for Barrel VRD treatment	To ensure enrollment of appropriate candidates
Exclusion criteria	Minor revision the INR and known anti-coagulant/antiplatelet agents requirement	Administrative change for clarity
Exclusion criteria Post-placement Antiplatelet Agents	Specified antiplatelet regimen dose and duration	To standardize dual antiplatelet therapy in the study
Secondary Endpoints	Change from number/percentage of “device deployments” to “device implants”	For accuracy in reporting device success
Secondary Endpoints	Change from the percentage of patients with mRS of 0-2 to also include patients with no change from baseline	Patients with no worsening from baseline should also be included in an analysis of good outcomes
Schedule of Tests Study Evaluations	Added 180 day visit, widened 30 day visit window from $\pm 7$ days to $\pm 14$ days and allowed 30 day visit to be conducted via phone, added unscheduled visit and screening blood labs; added guidance for the medications to be collected	To increase patient oversight and provide more specific instructions for unscheduled visits and medication collection
Enrollment	Updated definition to specify that enrollment occurs at the point of consent	For clarity
Statistical Analysis Sets	Intention-to-treat (ITT) population definition changed from those treated with Barrel VRD to those who underwent attempted deployment of the Barrel VRD	To include all subjects with an attempt to be treated into the ITT population
Analysis of Primary Safety Endpoint	Safety threshold lowered from 20 to 15%	Change made per recommendation noted in FDA letter dated 11 Jun 2014; rates based on incidence in published literature
Procedure	Added instructions from Instructions for Use to address coiling: refined data to be recorded during the procedure	Administrative change for clarity and to ensure that all important procedural data are captured by the investigator and/or Core Lab
Termination of Subject	Added section describing potential reasons and	Administrative change for clarity

Revision A to Revision B		

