## 6.7 Analysis of Secondary Endpoints

Secondary endpoints will be analyzed with descriptive statistics along with a 95% confidence interval. Descriptive statistics for categorical variables will include the number and percentage of subjects in each category, with two-sided 95% confidence intervals of the percentage of subjects in each category. Descriptive statistics of continuous variables will include sample size, mean, standard deviation, minimum, maximum, and 95% confidence interval of the mean.

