#### 8.1.2 Secondary Endpoints

- Any cause death within 30 days or neurological death within 12 months  $\pm$  8 weeks.
- Number of Barrel® VRD treated aneurysms achieving Raymond Grade I or II at 12 months  $\pm$  8 weeks in the absence of retreatment, parent artery stenosis ( $> 50\%$ ), or target aneurysm rupture.
- Number and percentage of successful device implants
- Angiographic evidence of in-stent stenosis at 12 months  $\pm$  8 weeks reported according to the following ordinal groups:  $<25\%$ ,  $25-50\%$ ,  $51-75\%$ ,  $>75\%$ .
- Device-related Serious Adverse Events (SAEs).
- The composite percentage of patients with modified Rankin Score of 0-2 or no change from

baseline at 12 months  $\pm$  8 weeks.

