### 9.2 Patient Inclusion Criteria

A subject who meets all of the following criteria may be included in the trial:

1. Male or female between 18 and 85 years old.
2. A wide-neck aneurysm with a neck  $\geq$  4mm or a dome-to-neck ratio  $<$  2, that is also a bifurcating or branch MCA or basilar aneurysm and de novo or non-de novo MCA or basilar aneurysm where no stent was utilized.
3. Subject's aneurysm arises from a parent vessel with a diameter  $\geq$  2mm and  $\leq$  4mm.
4. Appropriate informed consent obtainable as determined by local IRB.
5. Life expectancy  $>$  24 months.

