### 9.3 Patient Exclusion Criteria

A subject who meets any of the following criteria will not be included in the trial:

1. Aneurysm rupture within 30 days of enrollment.
2. MCA or basilar bifurcating aneurysms not treatable with coiling.
3. Subject with anatomy not accessible for Barrel VRD treatment.
4. Aneurysm neck  $>$  8 mm.
5. Subject presents with an intracranial mass or is currently undergoing radiation therapy for carcinoma of the head or neck region.
6. Subject has additional aneurysms for which treatment is planned within 18 months.
7. Subject has platelet count of  $<$ 70,000.
8. Subject has had a previous intracranial stenting procedure associated with the target aneurysm.
9. Subject has an International Normalized Ratio (INR)  $\geq$  1.7 or is on one of the following anti-coagulant/anti-platelet medications: Aggrenox, Cilostazol, Apixaban, Dabigatran, Fondaparinux, Lepirudin, Pradaxa, Rivaroxaban, Argatroban, Arixtra.
10. Subject has serum creatinine level  $>$  2mg/dl at baseline screening.
11. Subject has known allergies to nickel-titanium metal.
12. Subject has known allergies to aspirin or heparin.
13. Subject has a life-threatening allergy to contrast (unless treatment for allergy can be tolerated).
14. Subject has a known cardiac disorder, likely to be associated with cardioembolic symptoms such as atrial fibrillation (AFIB).
15. Subject has any condition, which in the opinion of the treating physician, would place the subject at a high risk of embolic stroke.
16. Subject is currently participating in another clinical research study.
17. Subject is pregnant or breastfeeding.

18. Subject has participated in a drug study within the last 30 days.
19. Subject cannot or is unwilling to take ASA and a P2Y12 Platelet Inhibitor as required by the protocol following the procedure.
20. Subject is unable or unwilling to comply with protocol requirements and obtain required clinical evaluations and follow-up.

Before any subject is enrolled in the study, the baseline angiogram will be reviewed by a Barrel expert to ensure that the target intracranial aneurysm (IA) is amenable to treatment with the Barrel VRD device.

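### The secondary mRS endpoint credits an unchanged score but not an improved one, so a subject going from 5 to 3 is not a good outcome while one who stays at 5 is (minor)

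*Protocol*

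**What the plan says.** Protocol Section 3 (Study Synopsis) lists as the last of six secondary endpoints the percentage of patients with "modified Rankin Score of 0-2 or no change from baseline at 12 months ± 8 weeks". Section 8.1.2 gives the same rule: "The composite percentage of patients with modified Rankin Score of 0-2 or no change from" baseline at 12 months. Nowhere does the protocol define an unchanged score to include an improved one.

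The second condition entered at Revision B. Section 4.1 gives the reason: "Patients with no worsening from baseline should also be included in an analysis of good outcomes". Revision C reworded other secondary endpoints and left this one as it was.

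Section 6.7 sets the analysis: "Secondary endpoints will be analyzed with descriptive statistics along with a 95% confidence interval". No hypothesis, comparator or threshold is attached to the mRS endpoint.

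The mRS is scheduled at baseline, 30 days, 180 days and 12 months (Tables 3-1 and 12-1). None of the criteria in Sections 9.2 and 9.3 limits baseline mRS. Rupture is a bar only if recent: "Aneurysm rupture within 30 days of enrollment".

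**The concern.** The rule has two conditions joined by *or*: a 12-month score of 0 to 2, or a 12-month score equal to baseline. A subject who enters with substantial disability and improves, but not as far as 2, satisfies neither. A subject who enters with the same disability and does not improve satisfies the second. The endpoint therefore ranks some improvements below no improvement.

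This is a stated rule that misclassifies, and not detail left for later. An analysis plan that follows the protocol reproduces the misordering. One that codes the variable as no worsening departs from the protocol's definition. Two analysts could report different rates from the same data, and the choice might be made after the data are seen. What is at stake is the accuracy of the trial's only mRS-based endpoint, as a descriptive rate.

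**Working it through.** The protocol states no expected rate, power or threshold for this endpoint, so there is no figure to reproduce. The check is an enumeration.

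**Inputs**
- Baseline mRS *b* from 0 to 5, with no entry limit (Sections 9.2 and 9.3).
- 12-month mRS *f* from 0 to 6.
- Planned numbers: 119 treated or attempted, 107 evaluable after 10% loss to follow-up (Section 6).

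**Rules compared**
- As written: good if *f* ≤ 2 or *f* = *b*.
- As the Revision B rationale describes: good if *f* ≤ 2 or *f* ≤ *b*.

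**Result over the 6 × 7 = 42 pairs.** The rules differ on three pairs and agree on the other 39.

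| Baseline to 12 months | As written | No worsening |
|---|---|---|
| 3 to 3 | good | good |
| 4 to 4 | good | good |
| 4 to 3 | **not good** | good |
| 5 to 5 | good | good |
| 5 to 4 | **not good** | good |
| 5 to 3 | **not good** | good |

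All three differences arise at baseline 4 or 5. At baseline 3 any improvement reaches 0 to 2 and already counts. At baseline 0 to 2 the two rules are identical. Every difference moves from not good to good, so the written rule can understate the rate and can never overstate it.

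**Size per affected subject**
- 1/107 = 0.93 percentage points.
- 1/119 = 0.84 percentage points.

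Subjects in whom delivery was attempted without implant leave after the 30-day visit (Sections 12.6.5 and 12.6.7) and have no scheduled 12-month mRS. The 107 figure is therefore the more natural denominator.

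**How many subjects.** The protocol does not say. As an illustration only, assume that 2% to 10% of subjects enter at mRS 4 or 5, and that 10% to 50% of those improve but stay above 2:
- Low end: 0.02 × 0.10 = 0.2 percentage points, or 0.002 × 107 = 0.2 subjects.
- High end: 0.10 × 0.50 = 5 percentage points, or 0.05 × 107 = 5.4 subjects.

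The low end amounts to nobody. Neither assumed range has support in the protocol.

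**The case against.** The strongest reply is that nothing the trial decides depends on this endpoint. It is secondary and descriptive, and the primary efficacy test, the primary safety criterion and the sample size do not use mRS. That stands, and it is why the point is minor.

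A second reply is that the affected group is narrow. Improvement to 0 to 2 already counts, and subjects at mRS 4 or 5 may be rare, given the requirements on life expectancy and on compliance with follow-up. This also stands. Eligibility shows that such subjects could enroll, not that they will.

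A third reply is that Section 4.1 already records the intended meaning, so a statistician would code the variable correctly. The recorded reason does lower the risk of miscoding. It does not remove it, because the operative definition in Sections 3 and 8.1.2 says something narrower. The log is used here only as evidence of intent; a difference between it and the current text is not itself the error.

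A reader might go further and infer that the endpoint is biased against the device, or that several percentage points will be lost. The documents support neither. The study has one arm and this endpoint has no comparator or performance goal, so there is no device comparison to bias. Any total effect on the rate rests on an assumed baseline distribution.

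**Conclusion.** The endpoint is wrong as written, and the matter is minor. On the literal wording, 5 to 4, 5 to 3 and 4 to 3 are scored as not good, while staying at 4 or 5 is scored as good. This follows from the wording alone and needs no assumption about who enrolls.

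The practical effect is an understatement of one descriptive percentage, with the per-subject size given above and an unknown, possibly zero, number of subjects. No primary conclusion, alpha or sample size is affected.

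**What to change.** In Sections 3 and 8.1.2, replace the condition of no change from baseline with: *no worsening from baseline (12-month mRS less than or equal to baseline mRS)*. Leave the 0 to 2 condition as it is.

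The cost is a few words in two places. Baseline and 12-month mRS are already collected, so no visit, data item or sample size changes. The edit should be made before the 12-month data are analyzed, so that the coding is not chosen with results in view.

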**Table 3-1 Schedule of Tests**

Tests and Evaluations	Screening/ Baseline	Procedural (Day 0)	30 days ±14 days	180 days ±30 days	12 months ±8 weeks	Unscheduled Visit
Inclusion/Exclusion	X					
Demographics	X					
Medical history	X					
Medications	X	X	X	X	X	X
Blood Labs	X					
Modified Rankin Score	X		X	X	X	
NIHSS Score	X			X	X	X 
Adverse Events		X	X	X	X	X
Angiography 	X 	X		X 	X	
Raymond Grade Scale	X 	X		X	X	

MRA is acceptable if performed according to the standard of practice at the participating institution.

The baseline angiogram must be taken no more than 180 calendar days prior to the procedure.

For previously coiled aneurysms

If an angiogram is performed as standard patient care it should be sent to the core laboratory for analysis.

If visit is related to target aneurysm or potentially associated adverse event

## 4. Revision History

The below table lists the protocol revision history for the BARREL study:

**Table 4-1 Protocol Revision History**

Revision	Effective Date
A	March 10, 2014
B	February 20 th , 2015
C	May 18 th , 2016

### 4.1 Summary of Changes

Revision A to Revision B		
Section	Change	Rationale
Sponsor	Sponsor name and study contacts changed from Reverse Medical to Covidien Neurovascular	Covidien acquired Reverse Medical and is executing the study
Study Design	Increased the number of participating centers from 20 to 28	Updated to facilitate enrollment
Exclusion criteria	Added exclusion criteria for subject with anatomy not appropriate for Barrel VRD treatment	To ensure enrollment of appropriate candidates
Exclusion criteria	Minor revision the INR and known anti-coagulant/antiplatelet agents requirement	Administrative change for clarity
Exclusion criteria Post-placement Antiplatelet Agents	Specified antiplatelet regimen dose and duration	To standardize dual antiplatelet therapy in the study
Secondary Endpoints	Change from number/percentage of “device deployments” to “device implants”	For accuracy in reporting device success
Secondary Endpoints	Change from the percentage of patients with mRS of 0-2 to also include patients with no change from baseline	Patients with no worsening from baseline should also be included in an analysis of good outcomes
Schedule of Tests Study Evaluations	Added 180 day visit, widened 30 day visit window from $\pm 7$ days to $\pm 14$ days and allowed 30 day visit to be conducted via phone, added unscheduled visit and screening blood labs; added guidance for the medications to be collected	To increase patient oversight and provide more specific instructions for unscheduled visits and medication collection
Enrollment	Updated definition to specify that enrollment occurs at the point of consent	For clarity
Statistical Analysis Sets	Intention-to-treat (ITT) population definition changed from those treated with Barrel VRD to those who underwent attempted deployment of the Barrel VRD	To include all subjects with an attempt to be treated into the ITT population
Analysis of Primary Safety Endpoint	Safety threshold lowered from 20 to 15%	Change made per recommendation noted in FDA letter dated 11 Jun 2014; rates based on incidence in published literature
Procedure	Added instructions from Instructions for Use to address coiling: refined data to be recorded during the procedure	Administrative change for clarity and to ensure that all important procedural data are captured by the investigator and/or Core Lab
Termination of Subject	Added section describing potential reasons and	Administrative change for clarity

Revision A to Revision B		
Participation	process for termination of subject participation	
Core Lab	Clarified evaluations to be performed by the Core Lab. Added instructions for assessments of 6 month and unscheduled images as applicable. Removed requirement to use blinded third party	Administrative change for clarification and for consistency with standard process at Covidien
Adverse Events	Added ISO14155 definitions for adverse events. Updated severity definitions, updated relatedness categories, as well as device specific event and event reporting requirements	To clarify collection of adverse events and for standardization with Covidien processes
Adverse Events Risk Analysis	Moved anticipated AEs to the risk analysis section in the protocol and revised the list to align with the IFU	To align risks with IFU
Responsibilities	Rewrote the following sections to align with Covidien practices: CRFs, Document Retention, DSMB, CEC, Monitoring and Publications. Added the following sections: Ethical Conduct of Study, Institutional Review Boards, Quality Control and Quality Assurance	Administrative change for standardization with Covidien processes
Appendices Informed Consent Protection of Human Subjects	Removed appendices (instructions for use and sample consent form) from protocol	Administrative change; these documents are controlled outside of the protocol

Revision B to Revision C		
Section	Change	Rationale
Sponsor	Sponsor name changed from Covidien Neurovascular to Medtronic Neurovascular	Medtronic acquired Covidien and is executing the study
Inclusion / Exclusion Criteria	Removed Prasugrel, Ticagrelor, and Ticlid from the disallowed concomitant medications list	To allow for physician standard of care prior to the procedure and align with protocol requirements of any P2Y 12 inhibitor post procedure
Inclusion / Exclusion Criteria	Removed the requirement of non-allergy to clopidogrel and ticlopidine.	Clopidogrel is no longer a protocol required medication.
Inclusion / Exclusion Criteria	Changed the requirement from “subject cannot or is unwilling to take ASA/Clopidogrel” to “Subject cannot or is unwilling to take ASA and a P2Y 12 Platelet Inhibitor”	To align with revised dual anti-platelet therapy requirements
Primary Endpoints	Changed primary endpoint language from “absence of neurological death/major ipsilateral stroke...” to “incidence of neurological death/major ipsilateral stroke”.	Corrected the primary endpoint language for alignment with the primary safety endpoint a priori threshold of 15%
Secondary Endpoints	Changed secondary endpoint language from “absence of any cause death within 30 days...” to “Any cause death within 30 days...”	To remain consistent with primary endpoint format
Secondary Endpoints	Added language to secondary endpoint indicating stenosis will be evaluated at 12 months ± 8 weeks	Added for completeness as the timing of this endpoint had not been explicitly specified.
Secondary Endpoints	Changed secondary endpoint language from “absence of device-related serious adverse events...” to “device related serious adverse events...”	To remain consistent with primary endpoint format

Revision B to Revision C		
Section	Change	Rationale
Sample Size Calculation	
 
The primary performance goal was increased from 23% to 28%.
 
The estimated success rate of the trial was increased from 33% to 41%, therefore decreasing the necessary sample size to achieve 80% power for the trial.
 
Maintaining the assumption of a 10% dropout rate, the number of subjects required for the study changed from 164 to 119.
 
The maximum number of enrolled/consented subjects was specified as 159 to allow for screen fails.
 
	
 
In conjunction with increasing the performance goal, the estimated success rate of the trial was also increased and the corresponding sample size recalculated. Based on higher estimated success rate, sample size is being reduced.
 
The maximum number of subjects enrolled/consented was specified to account for up to 25% of subjects who consent for the trial and may withdraw prior to treatment or are determined to be ineligible.
 

Statistical Analysis Sets	
Removed: Note that in the case of missing primary efficacy endpoint data, the subject will be considered a failure in the primary efficacy endpoint analysis.
 
Added: The primary analyses for both the safety and effectiveness endpoints will be based on the observed data.
	
Considering missing data as failure, known as the imputing worst case scenario, is an extreme imputation form and is not appropriate for the primary statistical analysis. Instead, we plan to perform primary statistical analysis based on observed cases.

Handling of Missing Data	
Replaced tipping analysis for missing data with Multiple imputation technique and explanation of handling subjects who withdraw prior to the final assessment will be handled using the Markov Chain Monte Carlo algorithm to specify missing at random.
	
As recommended by FDA, we will apply multiple imputation technique to handle missing primary endpoints.

Post-Placement Anti-platelet Agents	
Changed the dual anti-platelet therapy requirement from a minimum of 325mg of Aspirin for 12 months and 75mg of Clopidogrel daily for 3 months to the minimum of 81 mg of Aspirin for 12 months and any P2Y12 platelet inhibitor for 3 months.
	
The standard of care for dual antiplatelet therapy varies across US institutions. This protocol has been updated to provide additional flexibility to investigators such that they may utilize antiplatelet regimens that are closer to their standard of care while also maintaining standardization of minimum antiplatelet requirements (minimum of two antiplatelet agents, minimum dosage and minimum duration) to prevent a wide variation in antiplatelet regimens in the study.

Follow-up Visits	
Added descriptions to the 30-day and 180-day follow up visits
	
Administrative update to provide a clearer presentation of visit requirements. There have been no changes to the visits or assessments required.

Revision B to Revision C		
Section	Change	Rationale
Study Exit  Subject Discontinuation by Investigator	Included statement regarding the requirement for follow-up through the 30-day visit for subjects who are enrolled and undergo an attempt delivery with the Barrel VRD but are not implanted  This existing statement was clarified in the 'subject discontinuation by investigator' section	This requirement was added to the study exit section and revised in the 'subject discontinuation by investigator' section for clarity. The purpose for this requirement is to ensure adequate safety follow-up for subjects who do not receive the Barrel implant.
Adverse Events	Updated relatedness definitions and added definitions for select neurological adverse events of interest	To clarify collection of adverse events and for standardization with Medtronic processes
DSMB Committee	Reference to DSMB stopping rules and interim analyses have been removed	Administrative change to reflect current DSMB Charter and no plan for an interim analysis.
Clinical Events Committee	Updated types of events to be reviewed to include: 1) all Adverse Events associated with a change in NIHSS (vs. only those with a sudden neurological worsening or deterioration $\geq 3$ points on the NIHSS) and 2) any Adverse Event related to the Antiplatelet Therapy	Expanded scope of adverse events to be adjudicated by the independent Clinical Events Committee for increased oversight
Multiple	Corrected spelling, grammatical, and formatting errors throughout the document	Administrative change for clarity

